During recruitment, we will initially screen Veterans by phone. Those that are eligible for the study based on the phone screen will be brought to the lab for consenting, intake, and baseline assessments (approximately 200 Veterans). However, we assume a portion of those individuals will not qualify for the study. That will leave us with approximately 150 Veterans (75 per condition) to randomize to treatment. For recruitment, we will utilize the VASDHS system of PTSD clinics, spanning the main and 3 satellite facilities, and general outpatient mental health clinics. VA employees are not the target population, however they will not be excluded if they meet the inclusion criteria.

Financial Incentives: Participants will be compensated for their time after each completed assessment. Veterans will receive \$50 for the baseline assessment (\$30 for completion of the questionnaires and

neuropsychological assessment, \$20 for the fMRI assessment), \$30 as a bonus for completing at least 80% of the cognitive training (or placebo word games), \$50 for the post-computerized training assessment, and \$70 for the post-therapy assessment (Total possible = \$200).

Procedures:

Design and methods: Veterans will be randomized to either 12 weeks of CEFT-CPT or placebo word training plus CPT. Assessments will be administered three times: at baseline, immediately after CEFT or word training (prior to CPT), and after CPT completion. Assessment of PTSD diagnosis, symptom severity, quality of life, and subjective and objective measures of cognition will be administered at baseline (prior to computerized training onset), immediately after completing the cognitive training portion of the study (i.e., 6 weeks after baseline, just prior to starting CPT), and after completion of CPT treatment (approximately 6 weeks later, a total of 12 weeks after study initiation). Treatment satisfaction will be assessed after CEFT and CPT completion. Symptom severity will also be assessed at the midway point for the cognitive training and weekly during the CPT intervention component. Functional neuroimaging during rest and during two well-validated EF tasks will be collected at baseline, a Go-No Go Task that taps inhibition and an N-Back Task that taps working memory.

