Treatment Randomization: Following baseline assessment, participants will be randomized to the experimental (CEFT-CPT) or control condition (WT-CPT). A computer-generated randomization sequence will be provided by our statistical expert [name] (consultant). Randomization will be stratified by gender to ensure a balanced number of males and females are in each treatment group. Participants, the study assessor, and therapists will be blinded to the experimental treatment condition.

Post-Intervention Assessments (3-4 hours): The full battery of self-report questionnaires measuring psychiatric symptoms, quality of life, and subjective cognitive functioning, objective measures of neuropsychological functioning, and structured clinical interview for PTSD diagnosis will be re-administered twice, once after cognitive training completion and again after CPT completion. For the neuropsychological tests, alternate forms will be used where available and the RCT design will distribute any practice effects equally across the two groups. Participants will also complete the two EF tasks again that were administered at baseline during neuroimaging (though fMRI will not be collected again) or during the baseline assessment if they did not undergo fMRI for safety reasons.

Assessment Measures:

Symptom Measures:

- **PTSD:** The Clinician-Administered PTSD Scale DSM 5 (CAPS-5; Weathers et al., 2013) is the gold-standard, semi-structured interview that corresponds to DSM-5 criteria for PTSD. The CAPS-5 shows strong reliability and validity.

PTSD Checklist for DSM-5 (PCL-5; Weathers, Litz, Keane, Palmieri, Marx, & Schnurr, 2013) will be used to regularly assess PTSD symptomatology at several points throughout the study. The PCL-5 is a 20-item self-report measure of PTSD symptoms with good psychometric properties. The PCL-5 maps directly onto DSM-5 diagnostic criteria.

- **Depression:** Beck Depression Inventory-II (BDI-II; Beck, Steer, & Brown, 1996) is a 21-question multiple-choice self-report inventory, one of the most widely used instruments for measuring depressive symptoms.
- **Subjective day-to-day executive functioning:** Behavior Rating Inventory of Executive Function (BRIEF; Guy et al., 2004) is an ecologically sensitive 75-item self-report questionnaire that measures several aspects of EF in an individual's everyday life in the last month, including inhibition, shifting, working memory, planning/organizing, emotional control, etc.

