Data Analysis: Data management and analysis will be supervised by [name] (Biostatistician and consultant). Data will be analyzed from all randomized subjects on whom we have a baseline assessment and at least one post-baseline evaluation. Every attempt will be made to obtain at least one follow up assessment on any individuals who drop out of treatment. Data will be screened for outliers, missing values, and violation of statistical assumptions. Preliminary analyses will be used to examine the descriptive statistics of the study sample and assess for the influence of outliers and non-normally distributed variables for possible exclusion or transformation. Gender, age, medications, depression, and TBI-related variables will be examined for differences between groups at baseline; they will be added as covariates if differences are significant.

Missing Data: Missing data values will be minimized by intensive training of the staff in techniques of clarifying answers and checking questionnaires while Veterans are on-site. When missing values are identified, several approaches to acquire the necessary data will be employed including 1) contacting the Veterans to obtain the missing data and/or 2) examining the missing data to assess randomness. We expect missing data to be randomly distributed. Missing data (i.e., loss to follow up) will be tested to determine if it is informative, and the methods developed by Diggle (1989) and Ridout (1991) to test for completely random dropouts will be applied. We will test whether the drop-outs are random or systematic by comparing the drop-outs with the study completers on the baseline data. An absence of significant differences would support the random nature of drop-outs. If the extent of missing data is small and the data appear to be consistent with a missing-at-random model (MAR), then the maximum-likelihood analysis using all randomized cases and the observed data is an appropriate method for handling the missing data.

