Analyses will be conducted using multilevel modeling (MLM; also known as hierarchical linear modeling and linear mixed effects modeling). MLM has several advantages over more traditional analytic approaches such as change scores or repeated measures ANOVAs, as it allows for the inclusion of participants who have missing data and who dropped out of the study prematurely without using data imputation or biased procedures that often reduce power, such as casewise deletion. MLM also accounts for the fact that repeated observations across time are not independent but are nested within individuals. This method can provide an estimate of the individual variability around the population trend, the variability of the individual intercepts (baseline symptom levels) and slopes (change in symptoms across time), and the correlation between them. Initial model testing will be conducted to determine whether including individual-level random effects of intercept and slope (to model variability in initial symptom level and variability in response to treatment) will improve model fit. In addition to including the significant random effects, the model will include the fixed effects of treatment group, time, and group-by-time interaction. Data will be analyzed from all randomized subjects (full intent-to-treat sample) using all available data collected at the different assessment points.

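### The planned mixed model lets the randomized arms differ at baseline and does not adjust for the outcome's own baseline value, so its group-by-time test is valid but less precise than the collected data allow.

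*Combined protocol and SAP*

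**What the plan says.** The multilevel-model paragraph of Section 9, Data Analysis, says that "the model will include the fixed effects of treatment group, time, and group-by-time interaction". It describes what the model estimates as including "the variability of the individual intercepts (baseline symptom levels) and slopes (change in symptoms across time), and the correlation between them", and says the data will be analyzed "using all available data collected at the different assessment points". Baseline is therefore a response, and the group term is the arm difference at that visit.

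The Treatment Randomization paragraph says "Following baseline assessment, participants will be randomized to the experimental (CEFT-CPT) or control condition (WT-CPT"). The schedule is: "Assessments will be administered three times: at baseline, immediately after CEFT or word training (prior to CPT), and after CPT completion". The same section adds symptom scores midway through training and weekly during CPT.

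On covariates, Data Analysis says "Gender, age, medications, depression, and TBI-related variables will be examined for differences between groups at baseline", and "they will be added as covariates if differences are significant". Depression is on that list. The baseline values of CAPS-5, PCL-5, quality of life, BRIEF and the executive-function tests are not. No text sets the two arms to a common baseline mean. The plan does not give the coding of time, the contrast that carries the test, or the final covariance structure. Random intercepts and slopes are kept only if they improve fit.

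**The concern.** Because arms are assigned after the baseline assessment, any baseline difference between them is chance. A model with a free group term spends information estimating a quantity that the design sets to zero, and carries that chance difference in full into the estimated effect. With complete data at baseline, week 6 and week 12, the group-by-time contrast at the last visit is the difference between arms in mean change from baseline.

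At stake is the precision of every continuous outcome under Hypotheses 1a and 2a, in a trial of about 150 randomized Veterans. The baseline scores that would recover it are collected anyway.

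**Working it through.** **Inputs from the documents.** About 75 per arm (Section 9, Subject recruitment; Section 10). Full assessments at baseline, about week 6 and about week 12 (Section 9, Design and methods).

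**Assumed, because the documents give none of these.** Baseline-to-week-12 correlation rho from 0.3 to 0.7. Ratio k of week-12 SD to baseline SD from 0.8 to 1.4. For power only: a true effect of 0.4 SD and two-sided 5%. The plan states no power calculation, so there is none to reproduce.

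**Formulas, complete data, categorical visits.** With baseline SD 1, the variance of the week-12 arm difference is 2v/n, where n is the number per arm.
- Planned model (free baseline difference): v = 1 + k² − 2·rho·k, the change-score variance.
- Common baseline mean, or baseline as covariate: v = k²(1 − rho²).
- The difference between the two is (1 − rho·k)², so the share of variance lost is (1 − rho·k)² / (1 + k² − 2·rho·k). It is never negative, and it vanishes when rho·k = 1. With k = 1 it reduces to (1 − rho)/2.

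**Equal SDs (k = 1).** Power is Φ(0.4/√(2v/75) − 1.96).

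| rho | v planned | v common baseline | loss | power planned | power common baseline |
|---|---|---|---|---|---|
| 0.3 | 1.40 | 0.91 | 35% | 54% | 73% |
| 0.5 | 1.00 | 0.75 | 25% | 69% | 81% |
| 0.7 | 0.60 | 0.51 | 15% | 89% | 93% |

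At rho 0.5, for example, √(2 × 1.00/75) = 0.163 and √(2 × 0.75/75) = 0.141. In sample-size terms, the planned test on 150 has the precision of 150 × 0.75 = 112.5 participants under the better model.

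**Unequal SDs, loss at rho 0.3 / 0.5 / 0.7.**
- k = 0.8: 50 / 43 / 37%
- k = 1.2: 24 / 13 / 3%
- k = 1.3: 19.5 / 9 / 1%
- k = 1.4: 16 / 6 / 0%

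**Other model forms** (generalized least squares with the true covariance; exchangeable correlation and equal SDs unless stated). Variances here are n times the variance of the arm difference, that is, 2v.
- Linear time, three visits: the planned slope contrast again has the change-score variance. The loss is 40 / 27 / 16% at rho 0.3 / 0.5 / 0.7. With random intercept and slope, the cases tried lose between 10 and 28%.
- Weekly scores with linear time, rho 0.5: the planned model (1.2) beats the simple change score (2.0), but 29% is still lost.
- Monotone dropout of 20 to 40%, half the leavers going before week 6 and half after it: at 40% and rho 0.5 the planned model (2.93) beats the completers' change score (3.33). The loss is 10 to 30% with categorical time and 12 to 36% with linear time.

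**Does removing the group term always help?** Only if the covariance is modelled adequately. Take three visits, rho 0.7, SD rising linearly to 1.3 times baseline, and a fitted random intercept alone:
- Group term kept: true v 0.87, type I error about 5.5%.
- Group term removed: true v 0.91, but the model reports 0.70. Type I error is 2Φ(−1.96 × √(0.70/0.91)), about 8.5%.

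An unstructured covariance avoids this.

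**The case against.** The planned model is standard and stays valid under randomization, so this is a question of efficiency. That stands. A reader might infer bias or an invalid test from the free baseline difference; nothing in the documents supports that.

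A reader might also infer that the plan contradicts itself, since it says "MLM has several advantages over more traditional analytic approaches such as change scores or repeated measures ANOVAs". It does not. Its reasons are retention of participants with missing data and proper handling of repeated measures, and on those grounds the preference is sound. It claims no gain from baseline adjustment. Nor is the test merely a change-score comparison in all circumstances: the identity is exact for complete data at the three main visits, and the mixed model does better with dropout or with weekly scores under linear time.

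The size is open too. Requiring a current PTSD diagnosis may narrow the baseline spread, and the plan allows for varying response to treatment. Both make a larger follow-up SD plausible, which pushes the loss toward zero when rho is high. Finally, simply deleting the group term from a random-intercept model can do harm, as shown above. That objection stands and shapes the fix.

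**Conclusion.** The point holds as one of efficiency. The model as written leaves free a baseline difference that randomization sets to zero, and no standing covariate recovers the lost precision. Under assumed values, the loss is about 15 to 35% of the variance for rho 0.7 to 0.3 with similar SDs, near 0 to 20% with a follow-up SD 1.3 to 1.4 times baseline, and 37 to 50% with one 0.8 times baseline. A reader might take a third as the most that could be lost, or as typical. It is neither, because the documents fix neither rho nor the SD ratio. The plan also does not name group-by-time as the main test; that is inferred from Hypothesis 2a, which concerns greater improvement. The change is worth making before outcomes are compared by arm.

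**What to change.** For the continuous outcomes at baseline, week 6 and post-CPT, replace the fixed effects with categorical visit plus group-by-visit terms at the two post-baseline visits only. There is then no group main effect and one baseline mean for both arms. Specify an unstructured within-person covariance, not a random intercept alone. Name the post-CPT group difference as the main contrast. Say separately how the weekly PCL-5 scores enter.

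Alternatively, keep the planned model form on post-baseline responses and add the outcome's baseline value, with its own coefficient at each visit, as a covariate whether or not the arms differ at baseline. This uses only Veterans with at least one post-baseline value, which the opening Data Analysis paragraph already specifies. The later statement that the full intent-to-treat sample is analyzed would need to agree with it.

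The cost is slightly more model specification. No new data, visits or patients are needed.

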2. Auditory Ace: auditory working memory exercise, essentially an N back task where auditory information is retained and manipulated to determine if the current card matches a card N steps back in the sequence
3. Card Shark: visuospatial working memory exercise, similar to the Auditory Ace, except the information used to determine matches is presented visually
4. Juggle Factory: visuospatial working memory exercise, participants reconstruct a sequence of numbers in moving circles in the correct order, at more difficult levels participants must inhibit the influence of distractors
5. Mixed Signals: inhibition exercise, participants respond if what they hear and see matches in a particular way (while ignoring irrelevant information), otherwise they withhold their response
6. Divided Attention: inhibition exercise, participants indicate whether two objects match on a particular aspect (e.g., shape, color, fill) while ignoring irrelevant/competing aspects

Placebo word games: Participants in the active control group will be assigned to complete computerized placebo game training at the same frequency as CEFT. *Games and puzzles will be accessed online via BrainHQ in a similar manner to the CEFT condition.* This placebo condition controls for the effects of computer exposure, contact with research staff, and monetary payments. In addition, it controls for nonspecific engagement and motivation through the reinforcement of graphics-based computer games but does not provide the constrained, intensive, adaptive training of specific executive functions that the active condition provides. Participants will rotate through a series of games (e.g., *sudoku*, *crossword*, *connect four*) for the same number of hours as the EF training condition. After 6 weeks of game training, they will also receive CPT-C as detailed below.

Cognitive Processing Therapy: CPT is an evidence-based, trauma-focused therapy for PTSD endorsed by the VA/DoD Practice Guidelines and is widely available within VASDHS. Patients will receive a well-validated version of CPT, CPT-Cognitive only (CPT-C), which is a standard PTSD treatment provided at the VA that differs from the original version of CPT in that it does not include written trauma accounts. It entails 12 visits to the VA, each lasting 50 minutes.

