- For multisite studies, provide the total number of subjects from all sites and include description of the local site's role as a coordinating center if applicable.
- Indicate the number of VA participants to be studied.
- Indicate the estimated number of consented subjects that will fail the screening process, if any.

Participants: The study specifically targets Veterans with PTSD and cognitive complaints. During recruitment, we will initially screen Veterans by phone. Those that are eligible for the study based on the phone screen will be brought to the lab for consenting, intake, and baseline assessments (approximately 200 Veterans). However, we assume a portion of those individuals will not qualify for the study. That will leave us with approximately 150 Veterans (75 per

condition) to randomize to treatment. For recruitment, we will utilize the VASDHS system of PTSD clinics, spanning the main and 3 satellite facilities, and general outpatient mental health clinics. The TBI Polytrauma Clinic and TBI Cognitive Rehabilitation Clinic will also be used as a source of recruitment since the majority of Veterans presenting to these clinics have comorbid PTSD. VA employees are not the target population, however they will not be excluded if they meet the inclusion criteria.

2. Inclusion/Exclusion Criteria:

Inclusion criteria are: 1) OEF/OIF Veterans enrolled at VASDHS, 2) aged 18-55 3) current PTSD diagnosis, 4) endorsement of cognitive complaints, 5) no pending medication changes, 6) English-speaking.

Exclusion criteria include: 1) active substance use disorder in the last month, 2) suicidal intent or attempt within the last month, 3) schizophrenia, psychotic disorder and/or bipolar disorder, 4) dementia, 5) premorbid IQ < 70, 6) participation in other concurrent PTSD intervention studies, 7) previous completion of more than 4 CPT sessions, 8) history of a documented neurological disorder (e.g., Parkinson's disease, multiple sclerosis, epilepsy) 9) moderate to severe TBI (loss of consciousness greater than 30 minutes or post-traumatic amnesia greater than 24 hours).

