The exclusion criteria involving specific DSM-5 (Diagnostic and Statistical Manual-5) disorders, including substance use disorder, schizophrenia, psychotic disorder, bipolar disorder, and dementia (criteria 1, 3, 4) will be determined based on a CPRS chart review for clinical assessments that determine diagnosis based on DSM-5 criteria. We will also ask them during the phone screen about diagnoses. If there is any ambiguity in terms of psychiatric diagnoses based on the phone screen and a review of patient records (CPRS) that would disqualify the participant, the relevant portions of the MINI International Neuropsychiatric Interview (MINI; Sheehan, 2014) will be administered during the baseline assessment to clarify eligibility, as noted in the methods section. CPRS will also be reviewed for evidence of suicide intent or attempt within the last month (criteria 2), including a review of their Comprehensive Suicide Risk Assessment (CSRA) documented in CPRS. We will also ask them during the baseline assessment, including during the completion of the Beck Depression Inventory-II (BDI-II) that has a question about suicidal intent. An endorsement of a 1 or higher on this item will prompt further assessment for intent as described in the suicidality form. Premorbid IQ below our cutoff (criteria 5) will be determined either by a chart review if the participant received a previous clinical neuropsychological assessment documented in CPRS or by administering the WRAT5 during the baseline assessment (see methods section). Criteria 6, 7, 8, 9 will be determined by a CPRS chart review and also based on participant answers to the relevant questions on the phone screen. If the severity of any TBIs experienced (criteria 9) is ambiguous, eligibility will be determined by the Ohio State University TBI Interview administered at the baseline assessment (see methods section).

Veterans will not be excluded for current psychotropic medication usage or past mental health treatment that was not CPT, but given the potential impact on outcome variables of interest, we will track duration and type of past mental health therapies as well as current medication use in enrolled Veterans.

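### Past therapy is tracked because it may affect outcomes, yet no efficacy analysis uses it: name it as a prespecified covariate (minor)

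*Combined protocol and SAP*

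**What the plan says.** **Collection.** Section 10 (Inclusion/Exclusion Criteria) does not exclude Veterans for current psychotropic medication or for "past mental health treatment that was not CPT". It continues: "given the potential impact on outcome variables of interest, we will track duration and type of past mental health therapies", and names current medication use in the same sentence for the same reason.

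**Prior CPT.** The exclusion reads "7) previous completion of more than 4 CPT sessions", so 0 to 4 earlier sessions are allowed. The Cognitive Processing Therapy text in Section 9 says of the course: "It entails 12 visits to the VA, each lasting 50 minutes". On how eligibility is checked, Section 10 says: "Criteria 6, 7, 8, 9 will be determined by a CPRS chart review and also based on participant answers". Prior CPT exposure is thus looked up before randomization.

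**Analysis.** Section 9, Data Analysis, gives the candidate covariates: "Gender, age, medications, depression, and TBI-related variables will be examined for differences between groups at baseline". The entry rule is "they will be added as covariates if differences are significant". Of the multilevel model it says: "the model will include the fixed effects of treatment group, time, and group-by-time interaction", with random effects added where they improve fit. Randomization is stratified by gender only.

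**Hypotheses (Section 6).** 2a concerns PTSD symptoms and quality of life. 2b concerns homework hours, sessions attended and treatment completion.

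**The concern.** One sentence in Section 10 gives one reason for tracking two variables. Medications reach the covariate list; past therapy does not. Because that list is closed, past therapy could not enter a model even if the arms differed on it significantly.

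The gap is most relevant to Hypothesis 2b. Symptoms and quality of life are measured at baseline, but sessions attended and completion have no pre-randomization value in this trial. Earlier therapy, including a partial exposure to CPT itself, is one of the few baseline facts that bears on them directly. If it is prognostic, leaving it out gives up precision, and a chance imbalance between arms stays in the reported difference.

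**Working it through.** The documents give no alpha, power, effect size, completion rate or share with prior therapy, so there is no figure of the plan's own to reproduce. What follows is illustration on assumed inputs.

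**Inputs**
- From the documents: about 150 randomized, 75 per condition.
- Assumed: share *w* with relevant prior therapy 10–40%; completion lower by *RD* = 10–30 points in that group; completion 50% vs 70% by arm; two-sided alpha 0.05.

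**1. Where the variable appears**

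| Place | Medications | Past therapy |
|---|---|---|
| Section 10, tracked for possible effect on outcomes | yes | yes |
| Section 9, candidate covariates | yes | no |
| Section 9, terms always in the model | no | no |
| Section 9, stratification | no | no |

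The nearest use of past therapy would be the comparison of drop-outs with completers on baseline data. That is a missing-data check, not an efficacy analysis.

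**2. Chance imbalance**

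SD of the difference in shares = √(2w(1−w)/75).
- w = 0.1: √(0.18/75) = 4.9 points.
- w = 0.4: √(0.48/75) = 8.0 points.

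Exact (hypergeometric) probabilities, with Fisher's test as the baseline test:

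| w | Gap ≥ 10 points | Gap ≥ 10 points and p ≥ 0.05 | Smallest significant gap |
|---|---|---|---|
| 0.1 | 2.7% | 0% | 12.0 points |
| 0.2 | 15.2% | 12.9% | 16.0 points |
| 0.3 | 15.4% | 12.2% | 17.3 points |
| 0.4 | 24.3% | 21.3% | 18.7 points |

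At shares of 20–40%, most gaps of 10 points or more would not be significant. Adding the variable to the list under the present entry rule would therefore usually leave it out of the model.

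**3. Effect of such a gap on the result**

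Shift in the observed arm difference = gap × RD. A 10-point gap gives 0.10 × 10 = 1 point up to 0.10 × 30 = 3 points. The standard error of the completion difference is √((0.25 + 0.21)/75) = 7.8 points.

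**4. Power for completion**

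Unadjusted: Φ(0.20/0.0783 − 1.96) = 72.4%. Adjustment removes w(1−w)RD² from each arm's variance:

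| w | RD = 10 points | RD = 20 points | RD = 30 points |
|---|---|---|---|
| 0.2 | 72.7% | 73.6% | 75.1% |
| 0.3 | 72.8% | 73.9% | 76.0% |
| 0.4 | 72.8% | 74.2% | 76.5% |

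The gain is 0.3 to 4.1 points. A simulation of 20,000 trials with a true effect of +20 points agrees. With w = 0.4 and completion 65% without the history and 30% with it, power rises from 72.9% to 78.0%. With w = 0.3 and 60% against 50%, it goes from 76.0% to 76.2%.

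**5. Continuous outcomes (Hypothesis 2a)**

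Variance explained = w(1−w)d²/(1 + w(1−w)d²), for a prognostic difference of d SD.
- w = 0.1, d = 0.3: 0.0081/1.0081 = 0.8%.
- w = 0.4, d = 0.5: 0.06/1.06 = 5.7%.

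For an assumed treatment effect of 0.46 SD, power is 80.4% unadjusted, 80.8% if the covariate explains 1% of variance and 82.4% if it explains 5%.

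**The case against.** **A reader might infer that Veterans with 1 to 4 earlier sessions are known CPT drop-outs, so that the plan ignores an earlier measurement of the Hypothesis 2b outcome.** The documents do not support that. Criterion 7 sets only a cap; it does not say why or when earlier sessions ended. Section 10 speaks of a potential impact on outcomes, not of non-completion. The tracking sentence opens with treatment other than CPT, and although prior CPT is checked for eligibility, nothing clearly says that the session count is kept for analysis. This part of the objection stands in full.

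**The gain is small, and the larger figures need a common and strongly prognostic history.** This also stands. Flyers go to patients newly accepted into the PTSD program, which makes a large share with earlier CPT doubtful, although other recruitment sources exist. With w = 5–10% and RD = 30 points, the formula in step 4 gives about 73.2–73.9%, against 72.4% unadjusted.

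**The real weakness is covariate selection by significance test, and Hypothesis 2b has no stated model for a binary or count outcome.** Both are fair. Step 2 shows that the entry rule would defeat a mere addition to the list, so the fix has to bypass it for this variable. The missing Hypothesis 2b model is a separate gap; any covariate has to be written into that model once it is specified.

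**Other baseline variables, such as executive function, could be argued for too.** True. Past therapy differs in that the protocol itself gives possible influence on outcomes as the reason for tracking it, and treats its companion in that sentence as a covariate candidate.

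**Conclusion.** The point holds as a minor one. The protocol tracks past therapy because it may influence outcomes and then gives it no place in the stratification, the covariate list or the model.

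The omission does not bias the treatment comparison. Randomization keeps the unadjusted estimate valid, and its standard error already allows for chance imbalance. The loss is some precision and some protection against an unlucky allocation: about 0 to 5 power points for completion, about 1–6% of variance for the Hypothesis 2a outcomes, and a shift of 1 to 3 points in the completion difference if a 10-point imbalance occurs. All of these rest on assumed prevalence and prognostic strength, which the documents do not give. If the variable is weakly prognostic or the history is rare, the benefit is close to nil.

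**What to change.** In Section 9, Data Analysis:
1. State that prior PTSD psychotherapy, including the CPT session count already checked for criterion 7, is recorded as an analysis variable and tabulated by arm at baseline.
2. Include it as one prespecified covariate in the Hypothesis 2a and 2b analyses, regardless of the baseline significance test. Code it any versus none. Use none / 1–4 CPT sessions / other PTSD therapy only if cell sizes allow, with that rule fixed before unblinding.

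No eligibility rule changes. The cost is a sentence or two, one coded variable from information already being gathered, one or two degrees of freedom, and a possibly sparse category under the three-level coding.
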